11.1.8. Adverse Events

An AE is any symptom, physical sign, syndrome, or disease that either emerges during the study or, if present at the start of the study, worsens during the study, regardless of the suspected cause of the event. Changes in conditions present at screening (defined as SV1 of the CVT-301-004E study for CVT-301-naïve and [CVT-301-009](#) patients and SV1 of the [CVT-301-004](#) study for [CVT-301-004](#) patients) and new symptoms, physical signs, syndromes, or diseases should be noted on the AE page of the eCRF during the study. For these AEs captured on the AE eCRF for CVT-301-naïve and [CVT-301-009](#) patients, AEs reported prior to the first study treatment at TV1 will be considered baseline AEs, and AEs reported from first treatment will be considered treatment-emergent adverse events (TEAEs).

AEs may be volunteered spontaneously by the patient, discovered as a result of general questioning by the study staff, or determined by physical examination. At each visit, the patient will be asked, “Have you experienced any problems since your last visit?” All AEs will be recorded on the eCRF. For all AEs, the investigator must pursue and obtain information adequate both to determine the outcome of the AE and to assess whether it meets the criteria for classification as a serious AE requiring immediate notification. Follow-up of the AE, even after the date of therapy discontinuation, is required if the AE persists until the event resolves or stabilizes at a level acceptable to the investigator.

In order to avoid vague, ambiguous, or colloquial expressions, all AEs should be recorded in standard medical terminology rather than the patient’s own words. Each AE will also be described in terms of duration, frequency, intensity, association with the study medication, assessment of possible causes, actions taken, and outcome, using choices given on the eCRF. Specific guidelines for classifying AEs by intensity and relationship to study medication are given in [Table 2](#) and [Table 3](#), respectively.

Table 2 Classification of Adverse Events by Intensity

MILD: An event that is easily tolerated by the patient, causing minimal discomfort and not interfering with everyday activities.

MODERATE: An event that is sufficiently discomfoting to interfere with normal everyday activities.

SEVERE: An event that prevents normal everyday activities.

Table 3 Classification of Adverse Events by Relationship to Study Medication

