Definitely not related: The AE is definitely not related to the drug. This designation should be reserved for those events which occur prior to study treatment or for those events which cannot be even remotely related to study participation (e.g., injuries sustained in an automobile accident as a passenger).

Unlikely related: There is no reasonable association between the study treatment and the suspected event and the event could have been produced by the patient's clinical state or other modes of therapy administered to the patient.

Possibly related: The suspected adverse event may or may not follow a reasonable temporal sequence from study treatment administration but seems to be the type of reaction that cannot be dismissed as unlikely. The event could have been produced or mimicked by the patient's clinical state or by other modes of therapy concomitantly administered to the patient.

Probably related: The suspected adverse event follows a reasonable temporal sequence from study treatment administration, abates upon discontinuation of the treatment, and cannot be reasonably explained by the known characteristics of the patient's clinical state.

Definitely related: This designation should be reserved for those events which have no uncertainty in their relationship to treatment administration.

When changes in the intensity of an AE occur more frequently than once a day, the maximum intensity for the experience should be noted. If the intensity category changes over a number of days, then those changes should be recorded separately (with distinct onset dates).

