12.5. Safety Analysis

The disposition of the patients will be summarized by tabulating the number of screened, randomized, completed, and discontinued patients. The reasons for premature discontinuations will be tabulated.

The extent of exposure to study treatment will be summarized for each dose level. For the patients who received CVT-301 treatment in the CVT-301-004 study, the total exposure will be the sum of exposure in the CVT-301-004 study and the CVT-301-004E study.

All AEs will be coded using the Medical Dictionary for Regulatory Activities (MedDRA) dictionary. The TEAEs (i.e., events which start or worsen during the study treatment) will be tabulated by treatment group, system organ class, and preferred term. Both patient and event counts will be calculated. In addition, the TEAEs will be evaluated by seriousness, severity, and causality to the study treatment. The AEs leading to a premature discontinuation or dose adjustment will also be summarized. The AEs will be summarized by dose level (CVT-301 DL1 or CVT-301 DL2). Descriptive statistics will be used to describe the overall incidence of TEAE normalized for duration of exposure (number of TEAEs divided by the total exposure to CVT-301 measured as patient years). Furthermore, the time of onset of the TEAEs will be summarized.

For vital signs, ECG parameters, spirometry, the changes from pre-dose to post-dose assessments of the corresponding day will be calculated and compared between the treatment groups using descriptive statistics. For spirometry and safety laboratory variables, the differences in pre-dose values between study days will be described. Furthermore, the changes in the spirometry values and difference between the groups (DL1/DL2 or patients treated with CVT-301/placebo in CVT-301-004) will be estimated using a Mixed Model for Repeated Measurements (MMRM) similar to the one used for the efficacy variables. The proportions of patients meeting ATS quality criteria (and also for those ‘rejected’) will be summarized. Changes from baseline to follow-up in the rating scales for assessing suicidality, somnolence, and impulse control disorders will be summarized descriptively.

At least the following variables will be analyzed:

- Vital signs: standard and orthostatic systolic and diastolic BP and HR.

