## Statistical Analysis Plan

### 2. PURPOSE

The purpose of this statistical analysis plan (SAP) is to ensure that the data listings, summary tables and figures which will be produced, and the statistical methodologies that will be used, are complete and appropriate to allow valid conclusions regarding the study objectives.

This SAP describes the statistical analysis as it is foreseen at the time of planning the study. The SAP will serve as a compliment to the study protocol and supersedes it in case of differences. In case of major differences between the study protocol and SAP (e.g. changes in the analysis related to the primary endpoint) protocol amendment will be considered. The SAP may be updated during the conduct of the study and will be finalized before the data base lock. However, the analyses defined after the blind of study CVT-301-004 has been broken will be considered as exploratory.

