### 9.4. ADVERSE EVENTS

All AEs will be coded using the MedDRA version 17.0.

Treatment-emergent adverse events (TEAEs) are defined as all AEs that start after the patient receives the first dose of CVT-301 after the relevant baseline (see Section 6.2 for the definition of baseline). Events will be classified as drug-related if the AE is classified as possibly, probably, or definitely related to study drug.

Events with a missing start time, but with a start date equal to the date of first dose of study drug will be considered treatment-emergent. If the AE start date is incomplete, then it will be imputed as follows for the purpose of determining TEAE:

- If the start date is completely missing, the start date will be equal to the first dose date. However, if the stop date is not missing and is before the first dose date, then the stop date will be used instead.

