## Statistical Analysis Plan

- If the start day is missing, the first day of the month will be used.
- If the start day and month are missing, then the first day of the first month (January) will be used.

The original date and time will be shown on all listings of AEs. Listings will be provided for all AEs, serious AEs, AEs leading to study drug discontinuation, AEs leading to dose reduction, and deaths.

TEAEs will be summarized by SOC and PT for each treatment group and CVT-301 overall. TEAEs with onset after the treatment period are attributed to the treatment group during the treatment period. Both event and patient counts, where applicable, will be summarized. The counts will be complemented by percentages will be calculated for the patient counts unless otherwise specified. In addition, the incidence of TEAEs, normalized for duration of exposure to CVT-301 will be presented (number of TEAEs divided by the total exposure to CVT-301, measured as patient years).

- An overall summary of the number and percentage of patients reporting TEAEs and the number of TEAE events, drug-related TEAEs, severe TEAEs, serious TEAEs, TEAEs leading to dose interruption, TEAEs leading to study drug discontinuation, TEAEs leading to dose reduction and TEAEs leading to death
- TEAEs by SOC and PT, both as event and patient counts
- TEAEs by PT, both as event and patient counts
- Drug-related TEAEs by SOC and PT, both as event and patient counts
- Severe TEAEs by SOC and PT, both as event and patient counts
- Drug-related TEAEs by SOC, PT and severity, as event counts; percentages will be calculated for the event count out of total number of events
- Drug-related TEAEs by SOC, PT and relationship, as event counts; percentages will be calculated for the event count out of total number of events
- Serious TEAEs by SOC and PT, both as event and patient counts
- TEAEs leading to study drug interruption, both as event and patient counts
- TEAEs leading to study drug withdrawal, both as event and patient counts
- TEAEs leading to dose reduction, both as event and patient counts
- Most common AEs, both as event and patient counts, most common TEAEs is defined any AE preferred term occurred in greater than 10% total patients
- Time to first onset of most common AEs, classified as 0-1 months, >1-3 months, >3-6 months, >6-9 months and after 9 months, where the date of TEAE onset will be used as the time point for classification

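### SAP 9.4 defines TEAEs by start date and does not link the intensity records of one AE, so one AE can count as several events and an easing pre-dose AE can count as treatment-emergent

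*SAP*

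**What the plan says.** **Recording.** Protocol 11.1.8 has two rules for AEs whose intensity changes. For changes spread over days: "If the intensity category changes over a number of days, then those changes should be recorded separately (with distinct onset dates"). Nothing limits this to worsening, so easing is covered too. For faster changes: "When changes in the intensity of an AE occur more frequently than once a day, the maximum intensity for the experience should be noted".

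**Definition.** SAP 9.4 states that TEAEs "are defined as all AEs that start after the patient receives the first dose of CVT-301", counted from the relevant baseline. It makes no comparison with pre-dose intensity. Protocol 12.5 describes TEAEs as "events which start or worsen during the study treatment". Protocol 11.1.8 defines an AE as something that emerges or, if already present, worsens. For CVT-301-naïve and CVT-301-009 patients it adds that "AEs reported prior to the first study treatment at TV1 will be considered baseline AEs".

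**Counting.** SAP 9.4 tabulates events and patients and gives an incidence computed as "number of TEAEs divided by the total exposure to CVT-301" in patient-years. The table of drug-related TEAEs by severity uses event counts only, with percentages of all events.

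**Precedence.** SAP 2 says: "The SAP will serve as a compliment to the study protocol and supersedes it in case of differences". SAP 11, which lists departures from the protocol, does not mention the TEAE definition.

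**The concern.** Each rule is reasonable alone. Together they let the number of events depend on how often an AE changed grade.

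SAP 6.3 names the exposure-adjusted incidence as its way of allowing for shorter follow-up in patients who stop early. Splitting one AE into several records raises the numerator of that rate and leaves exposure unchanged. Long, fluctuating AEs gain weight. In the severity table, added mild records dilute the moderate and severe share.

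The start-date rule also has no test for worsening. A condition present before the first CVT-301 dose that eases afterwards could be reported as emerging on treatment. That would reach further than the event tables. It could add a patient to a preferred term, count towards the 10% threshold for common AEs, and give a false date in the time-to-first-onset table. Opportunity for pre-dose records differs by source of patients: naïve and CVT-301-009 patients have a screening period of up to 35 days, while CVT-301-004 placebo patients have the whole of that study, with visits to Week 12. Such cases need not cancel in the tables broken down by treatment/study group.

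**Working it through.** The plan gives no AE count or rate to reproduce, so the check applies the rules to simple patterns.

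**Inputs.** Records are created as protocol 11.1.8 says: one per multi-day intensity step, each with its own onset date. The SAP 9.4 count is the number of records with onset after the first dose. The comparison counts one event per continuous AE. That event is treatment-emergent if it starts after the first dose, or if its post-dose intensity exceeds its pre-dose intensity (protocol 12.5). Each pre-dose pattern below has a single pre-dose record, so the highest and the last pre-dose grade are the same.

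| Course of one AE | SAP 9.4 as written | One event per AE |
|---|---|---|
| Moderate before dose, mild after | 1 | 0 |
| Severe before dose, then moderate, then mild after | 2 | 0 |
| After dose: mild, moderate | 2 | 1 |
| After dose: mild, moderate, mild | 3 | 1 |
| Mild before dose, severe after | 1 | 1 |

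In the last row the rules agree: a worsening gets its own onset date, and the start-date rule picks it up. They differ on improvement of a pre-dose AE and on repeated steps after dosing.

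**Effect on the rate.** Let p be the share of post-dose AEs with a multi-day intensity change and k the records per such AE. Exposure cancels, so the rate is multiplied by 1 + p(k − 1). The documents give neither p nor k. For assumed p from 5% to 30%:

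- k = 2: 1 + 0.05 × 1 = 1.05, up to 1 + 0.30 × 1 = 1.30
- k = 3: 1 + 0.05 × 2 = 1.10, up to 1 + 0.30 × 2 = 1.60

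These figures show how the rule behaves. They do not estimate what happens in this trial.

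**Effect on severity percentages.** A drug-related AE that goes mild, moderate, mild gives two mild records and one moderate, so 2/3 = 67% of its records are mild. Counted once at its maximum, it is one moderate event.

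**Effect on patient counts.** For an AE that began after dosing there is none: the patient is counted once per term however many records exist. A patient is added only when the sole post-dose record of a term is a lower-grade continuation of a pre-dose AE.

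**The case against.** The strongest objection is that protocol 11.1.8 asks for changes to be recorded separately but does not say that each becomes a new AE. Dated intensity entries under one AE would also comply, and the eCRF design is not in the documents. This stands as a caution: the over-count follows from the text as written but is not shown to occur in the data. It does not remove the need for a rule. If all grades sat under one AE with one start date, the over-count would vanish, but the start-date definition would then miss a pre-dose AE that worsened on treatment.

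Second, protocol 11.1.8 does not treat easing of an existing condition as an AE, and for naïve and CVT-301-009 patients it classes AEs reported before first treatment as baseline AEs. That weakens the pre-dose limb. But the same section has changes in conditions present at screening noted on the AE page, the baseline sentence does not name CVT-301-004 placebo patients, and the SAP classifies by start date.

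Third, the protocol's own wording varies. Its synopsis refers to TEAEs that start after baseline, close to the SAP. A reader might infer that the SAP has overturned one settled protocol definition. The documents show instead that several wordings were never reconciled.

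Fourth, the primary safety endpoint is spirometry, SAP 9.4 plans no AE test, and the rule is the same for both dose levels. A reader might infer that the dose comparison is biased; nothing in the documents shows that. Severe TEAEs also have their own table with patient counts.

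**Conclusion.** The point holds on the text. SAP 9.4, applied to records made under protocol 11.1.8, counts a post-dose AE once for each multi-day intensity step plus one. This affects the event counts, the per-patient-year rate and the event-based drug-related severity table. It also allows a pre-dose AE recorded again at lower intensity after dosing to be classed as a TEAE, against protocol 12.5 and the protocol's own definition of an AE. This second part is less certain, because it depends on whether sites open such a record.

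Three stronger readings are not supported. A reader might infer that every intensity change makes a new event, but changes within a day are recorded once at maximum intensity. A reader might infer that patient incidence is inflated generally, but for AEs that began after dosing it is not. And a reader might take the multipliers above as the expected inflation, when they only restate assumed values of p and k. The size of the over-count cannot be determined from the documents.

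The conclusion assumes that sites follow protocol 11.1.8 literally and that no linking exists in the eCRF. Neither document describes any.

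**What to change.** Amend SAP 9.4 as follows.

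- **Link.** Treat records as one event when they are intensity changes of the same continuous episode: same patient, same preferred term, differing intensity, and contiguous complete dates. Where dates are partial, or the records could be distinct episodes, confirm the link in blinded data review. Matching on preferred term and adjacent dates alone would merge separate short events, such as falls on consecutive days. It would also fail where SAP 9.4 imputes partial start dates to the first of the month or to January.
- **Describe.** Give the linked event its first onset date and its maximum post-dose intensity.
- **Classify.** Count an episode that began before the first CVT-301 dose as a TEAE only if its post-dose intensity exceeds its last pre-dose intensity. For CVT-301-004 placebo patients, take pre-dose records from the CVT-301-004 AE data. For an episode that qualifies this way, date the onset in the time-to-first-onset tables from the worsening, since its first onset precedes dosing.
- **Apply.** Use linked events for all event counts, Tables 14.3.2.2.5 and 14.3.2.2.6, the drug-related severity table and time to first onset. Listings keep every record.
- **Reconcile.** State one TEAE definition and record in SAP 11 any departure from protocol 12.5. If the eCRF already links records, say so.

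The cost is one extra derivation, access to CVT-301-004 AE data for the placebo patients, and a blinded review step. No new data collection is needed. Reported event counts will be somewhat lower.

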## Statistical Analysis Plan

- If the start day is missing, the first day of the month will be used.
- If the start day and month are missing, then the first day of the first month (January) will be used.

The original date and time will be shown on all listings of AEs. Listings will be provided for all AEs, serious AEs, AEs leading to study drug discontinuation, AEs leading to dose reduction, and deaths.

TEAEs will be summarized by SOC and PT for each treatment group and CVT-301 overall. TEAEs with onset after the treatment period are attributed to the treatment group during the treatment period. Both event and patient counts, where applicable, will be summarized. The counts will be complemented by percentages will be calculated for the patient counts unless otherwise specified. In addition, the incidence of TEAEs, normalized for duration of exposure to CVT-301 will be presented (number of TEAEs divided by the total exposure to CVT-301, measured as patient years).

- An overall summary of the number and percentage of patients reporting TEAEs and the number of TEAE events, drug-related TEAEs, severe TEAEs, serious TEAEs, TEAEs leading to dose interruption, TEAEs leading to study drug discontinuation, TEAEs leading to dose reduction and TEAEs leading to death
- TEAEs by SOC and PT, both as event and patient counts
- TEAEs by PT, both as event and patient counts
- Drug-related TEAEs by SOC and PT, both as event and patient counts
- Severe TEAEs by SOC and PT, both as event and patient counts
- Drug-related TEAEs by SOC, PT and severity, as event counts; percentages will be calculated for the event count out of total number of events
- Drug-related TEAEs by SOC, PT and relationship, as event counts; percentages will be calculated for the event count out of total number of events
- Serious TEAEs by SOC and PT, both as event and patient counts
- TEAEs leading to study drug interruption, both as event and patient counts
- TEAEs leading to study drug withdrawal, both as event and patient counts
- TEAEs leading to dose reduction, both as event and patient counts
- Most common AEs, both as event and patient counts, most common TEAEs is defined any AE preferred term occurred in greater than 10% total patients
- Time to first onset of most common AEs, classified as 0-1 months, >1-3 months, >3-6 months, >6-9 months and after 9 months, where the date of TEAE onset will be used as the time point for classification

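### The partial-date rule for adverse event onset moves events in the month or year of first dose to before dosing, so on-treatment events with such dates would be left out of every TEAE table

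*SAP*

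**What the plan says.** SAP section 9.4 defines treatment-emergence by onset: "Treatment-emergent adverse events (TEAEs) are defined as all AEs that start after the patient receives the first dose of CVT-301 after the relevant baseline". For incomplete dates it states: "If the AE start date is incomplete, then it will be imputed as follows for the purpose of determining TEAE". The imputed date therefore settles the classification. Three rules follow.

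- **No date at all:** "If the start date is completely missing, the start date will be equal to the first dose date". An exception follows: "However, if the stop date is not missing and is before the first dose date, then the stop date will be used instead".
- **Day missing:** "If the start day is missing, the first day of the month will be used".
- **Day and month missing:** "If the start day and month are missing, then the first day of the first month (January) will be used".

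The section also settles ties: "Events with a missing start time, but with a start date equal to the date of first dose of study drug will be considered treatment-emergent". The stop-date exception is attached only to the first rule. Neither partial-date rule refers to the first-dose date or the stop date.

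The protocol has no partial-date rule. Under SAP section 2 the SAP prevails where the two documents differ, so nothing elsewhere corrects these rules.

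**The concern.** The partial-date rules pick the earliest possible date. When the known month or year is that of the first dose, that date is nearly always before dosing, and the event drops out. A record with no date is kept as treatment-emergent, while a record correctly dated to the first-dose month is removed. More information gives the less cautious answer, which can hardly be intended.

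A likely source is SAP section 7.4, which has the same wording for medication dates. It does little harm there, because a medication with a stop date on or after first dose still counts as concomitant. The TEAE definition has no such second route.

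The rule also departs from protocol section 11.1.8. For CVT-301-naïve and CVT-301-009 patients, that section counts events reported from first treatment onwards as treatment-emergent.

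One flag feeds all the TEAE summaries: overall, drug-related, severe, serious, leading to interruption, discontinuation or dose reduction, per patient-year, and time to first onset. The last has a 0-1 month class, where missing-day losses would concentrate. SAP section 3.5 says the study size was chosen to supply safety data for regulatory submissions, so an error that can only remove on-treatment events matters.

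**Working it through.** The plan states no figure for this rule, so there is none to reproduce. The check applies the rules as written.

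**Worked case.** Take an illustrative first dose on 15 March 2016.

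| Recorded onset | Imputed onset | Class under SAP 9.4 |
|---|---|---|
| March 2016, day missing (true onset 20 March, stop 25 March) | 1 March 2016 | not TEAE |
| 2016 only (true onset 10 October) | 1 January 2016 | not TEAE |
| April 2016, day missing | 1 April 2016 | TEAE |
| 2017 only | 1 January 2017 | TEAE |
| Completely missing | 15 March 2016 | TEAE |

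In the first row the known stop date is after first dose, and the rule still does not use it.

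**Inputs for the size.** Treatment length is 364 days (SAP section 3.8: 52 weeks) or 392 days (protocol section 7: 56 weeks). For patients already on CVT-301 in CVT-301-004, whose baseline lies in that study, a further 12 weeks gives 392 + 84 = 476 days. Assumptions not in the documents: first-dose dates uniform over the calendar year, a constant event rate, and dates partial at random. All first-dose dates in one leap and one non-leap year (731 dates) were enumerated. An imputed date equal to the first-dose date counts as a TEAE.

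**How often the rule can fail.** The missing-day rule fails unless first dose fell on the 1st of a month: 707/731 = 96.7% of dates. The year-only rule fails unless first dose fell on 1 January: 729/731 = 99.7%.

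**Share lost.** For each first-dose date, the lost onset days run from the first-dose day to the end of that month (or year). They are zero when first dose is on the 1st (or on 1 January). The average is 14.74 days for a missing day and 182.25 days for a missing day and month. Share lost = average lost days / treatment length.

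| Length | Day missing | Day and month missing |
|---|---|---|
| 364 days | 14.74/364 = 4.05% | 182.25/364 = 50.1% |
| 392 days | 14.74/392 = 3.8% | 182.25/392 = 46.5% |
| 476 days | 14.74/476 = 3.1% | 182.25/476 = 38.3% |

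Among on-treatment events truly in the first-dose month with the day missing, 93.7% are lost. Among those in the first-dose year with only the year known, 99.5% are lost.

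**If events cluster early.** The onset distributions here are illustrative; the documents give none. The table shows simulated shares, with first doses spread evenly over a year and onset counted from the day after first dose.

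| Onset after first dose | Day missing | Day and month missing |
|---|---|---|
| Uniform over 12 months | 3.8% | 49.7% |
| Exponential, mean 60 days | 19.5% | 83.0% |
| Exponential, mean 30 days | 34.1% | 91.2% |

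Counting onset from the first-dose day itself changes these by no more than about 2 percentage points. All percentages in this section are shares of on-treatment events that already have that type of partial date. None is a share of all TEAEs.

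**The case against.** The best counter-argument is that few events may be affected. The first dose is taken under supervision, with adverse events monitored throughout the visit. Staff telephone 1 to 3 days later and again a week before TV2, which itself falls at 4 weeks. Protocol section 13.5 provides for full source verification and queries. The first-dose month is thus the most closely watched part of the study, a day is least likely to be missing there, and a year-only date for a new event is less likely still. The assumption that dates go missing regardless of time since dose may therefore overstate the loss, and the exponential scenarios are not taken from the documents. This stands: the absolute effect is unknown and could be zero.

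Three further points have some weight.

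- Events that arise during screening in the first-dose month are classed correctly by the present rule, and the shares above do not count them.
- Misflagged events are not lost from the report. Original dates appear in the listings of all adverse events, and serious events and deaths are listed for the All Available Population.
- The primary endpoints are spirometric, and the TEAE tables are descriptive.

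These points bear on how much harm the rule does. None of them makes it right. It resolves every doubt about a partial date in the first-dose month or year against treatment-emergence, and it treats a wholly unknown date more cautiously than a partly known one.

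**Conclusion.** The concern holds. Under SAP section 9.4 as written, an on-treatment event with a partial onset date in the first-dose month or year is classed as not treatment-emergent, except when first dose fell on the 1st of the month (or on 1 January for year-only dates). With evenly spread first doses, a constant event rate and dates partial at random, the loss over 364 to 476 days is 3.1% to 4.05% of on-treatment events with a missing day, and 38.3% to 50.1% of those with a missing day and month. It is larger if events cluster early. The number of partially dated events is not in the documents, so the effect on actual TEAE counts cannot be stated. For on-treatment events the error runs only towards under-counting. Because safety is the purpose of the study and the correction is simple, it should be made before database lock.

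**What to change.** Replace the two partial-date sentences in SAP section 9.4 with rules to this effect:

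- If the day is missing and the month and year are those of the first CVT-301 dose, impute the first-dose date.
- If the day and month are missing and the year is that of the first CVT-301 dose, impute the first-dose date.
- Otherwise use the 1st of the month, or 1 January.
- In every case, if a known stop date is before the first dose, the event is not treatment-emergent.

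For patients who took CVT-301 in CVT-301-004, the first dose is the one in that study. The reference to the relevant baseline already implies this, but it is worth stating.

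With this rule the enumerated loss is 0% for all three treatment lengths. The cost is two sentences and one derivation. The downside is that some truly pre-dose events from the same month or year, with no stop date or a later one, will be counted as TEAEs. That is the cautious direction, and the stop-date check limits it. The time-to-first-onset table should also say how imputed dates are used, since a year-only event set to the first-dose date would fall in the 0-1 month class.
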